### **Sample size calculation**

To determine the ideal number of participants, we have considered our first aim, which is to identify the variables linked to the CS phenotype that could help predict the response to treatment based on SMT for CLBP. In order to do this, we will perform a multiple regression analysis, using five independent variables as predictors, in particular the score on the pain catastrophizing scale (PCS) and central sensitization inventory (CSI) questionnaires (indicators of catastrophism and CS), the pressure pain thresholds (PPTs) in the primary pain area (marker of primary hyperalgesia), the urinary levels of the cytokine Tumor Necrosis Factor Alpha (TNF- $\alpha$ ; marker of inflammation) and finally the expectations of relief for each patient (indicative of potential placebo effects). The baseline values of these variables will be included in the multiple regression model. For each predictor variable, it is recommended to estimate about ten sample elements, therefore we predict that a sample size of 50 patients per group will be necessary (Ortega Calvo and Cayuela Dominguez, 2002). Taking into account two groups, one that will receive real SMT and the other placebo SMT, we will need a sample of 100 patients. An additional group of age and sex-matched healthy individuals without CLBP of the same size (50 participants) will be recruited to be used as a reference group, to determine

reference values in a healthy population for the predictor variables (questionnaires, PPTs, cytokines only)

Regarding the two main outcome variables (pain intensity and disability related to low back pain), we expect a reduction in pain and disability after one month in patients who receive 12 sessions of SMT compared to placebo. We aim to detect small to moderate effects since it is a one-month intervention in patients with chronic pain unresolved by other treatments over at least 3 months. Therefore, based on an effect size of  $f = 0.175$ , an alpha of 0.05, a power of 0.8 for 2 groups and 2 repeated measures (baseline and session 12), and a correlation between the repeated measures of 0.5, the size of the necessary sample is 34 patients per group and a total of 68 patients to detect statistically significant changes in clinical pain and disability. Therefore, our analysis based on the regression model to predict the clinical course provides us with a large enough size for both the first and second aims of this study.

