Official Title:

Efficacy of Chiropractic Spinal Manipulative Therapy in Patients With
Primary Chronic Low Back Pain: a Mechanistic Randomized Controlled
Trial

NCT number: Not Available

Unique Protocol ID: SMTCLBP

Date: December 15th, 2021

Statistical analyses

The normal distribution of the data will be verified using the Kolmogorov-Smirnov test. Data deviating from normality will be transformed to obtain a normal distribution before being entered into the data analysis. The two main outcome variables (clinical pain intensity and disability related to low back pain) will be compared between groups (SMT vs. placebo) over time (baseline and session 12) using a mixed analysis of variance. Average pain intensity since the previous treatment visit and in the seven days prior to the initial visit will be the variable used for statistical analyses. With an exploratory objective, the secondary variables (PCS, CSI, BDI-II, GAD scores, PPTs, degree of pain widespreadness, urinary cytokine levels, number and severity of reported adverse effects, presence of leg pain, pain medication use) will be compared between groups (SMT vs placebo) over time (baseline and session 12) using another mixed analysis of variance. To test a priori hypotheses, significant effects will be decomposed using planned comparisons. For the rest of the effects, Tukey's HSD will be used for testing any pair-wise comparisons between group means.

Pearson's product-moment correlation analyses will be carried out to examine the association between primary variables and secondary variables that demonstrate significant effects between groups over time. Subsequently, two multiple regression models will be used to examine the predictors of improvement in clinical pain and disability over time in patients who have received SMT, using secondary variables with a significant association with the primary variables. The secondary variables used for this analysis will be: baseline PCS and CSI score, baseline PPTs in the primary pain region, baseline TNF- α levels, and baseline expectations of pain relief. In addition, in another

regression model, the changes (delta) in these variables (except expectations of pain relief, since it is only measured at baseline) throughout the 4 weeks of treatment will be used as predictor variables. This is done to identify the variables most associated with clinical evolution, in order to answer the mechanistic question.

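### Does calling f = 0.175 small to moderate overstate the trial's sensitivity for SMT versus placebo?

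*Protocol*

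**What the plan says.** The Protocol's Sample size calculation section makes two calculations. The first, for the regression aim, uses ten patients for each of five predictors and gives 50 per group, so 100 patients. The second concerns the two primary outcomes, pain intensity and disability. There the authors write "we expect a reduction in pain and disability after one month in patients who receive 12 sessions of SMT compared to placebo", and add "We aim to detect small to moderate effects since it is a one-month intervention in patients with chronic pain". The inputs are f = 0.175, alpha 0.05, 80% power, two groups measured on two occasions, and a within-patient correlation of 0.5. The result is that "the size of the necessary sample is 34 patients per group and a total of 68 patients to detect statistically significant changes". The section concludes that the regression-based sample "provides us with a large enough size for both the first and second aims of this study".

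The SAP (Statistical analyses) says the primary outcomes will be "compared between groups (SMT vs. placebo) over time (baseline and session 12) using a mixed analysis of variance". Neither document names the group-by-time interaction as the effect that was sized, converts f into SD units or scale points, or states the difference detectable with 100 patients.

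**The concern.** Cohen's f does not mean the same thing for every effect in a repeated-measures design. For a comparison of two groups at one time point, the standardised difference is 2f, so f = 0.175 would be 0.35 SD. For the interaction in a two-group, two-occasion design, the difference in change is 4f, so the same f is 0.70 SD. A reader who sees the small-to-moderate label next to f = 0.175 may think the trial can detect about 0.35 SD between SMT and placebo, when the calculation supports twice that.

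What would be at stake is the reading of a non-significant primary result. At a correlation of 0.5, power for a 0.35 SD difference is 30% with 68 patients and 41% with 100. A null finding taken to rule out a difference of that size would be over-read.

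**Working it through.** **Inputs from the Protocol, Sample size calculation:** f = 0.175, alpha 0.05, power 0.80, 2 groups, m = 2 measures, rho = 0.5; N = 68 for the primary outcomes; N = 100 planned. **Test from the SAP, Statistical analyses:** a group-by-time mixed ANOVA. **Assumptions made here:** equal groups, a common SD at both time points, a two-sided test, no dropout unless stated, and a range of 0.3 to 0.7 for rho (the documents give only 0.5).

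**Step 1. Reproduce 68.** For the interaction, the F test has 1 and N − 2 degrees of freedom and noncentrality lambda = N × f² × m / (1 − rho), with f² = 0.030625.

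- N = 66: lambda = 66 × 0.030625 × 2 / 0.5 = 8.09, power 0.7997.
- N = 68: lambda = 68 × 0.030625 × 2 / 0.5 = 8.33, power 0.8116.

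So 68 is the smallest balanced total that reaches 80%, as stated. A between-group main effect averaged over time would need 196, and f defined from partial eta squared would need 262, so those readings are ruled out. The main effect of time uses the same formula and also gives 68, so the number alone does not identify the interaction.

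**Step 2. Translate f.** Let the four cell means be 0, 0, 0 and delta, in units of the SD at one time point. Each interaction deviation is ±delta/4, so f = delta/4 and delta = 4 × 0.175 = 0.70 SD. As a check, the SD of change is √(2 × (1 − 0.5)) = 1, and a two-sample t-test on change scores with 34 per group and a difference of 0.70 gives power 0.8116, the same value. Had the time main effect been sized, f = D/2, and 0.175 would be an average change of 0.35 SD.

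**Step 3. Test the claim that 100 patients are enough.** At f = 0.175 and N = 100:

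| rho | lambda | power |
|---|---|---|
| 0.3 (assumed) | 100 × 0.030625 × 2 / 0.7 = 8.75 | 0.834 |
| 0.5 (Protocol) | 100 × 0.030625 × 2 / 0.5 = 12.25 | 0.934 |
| 0.7 (assumed) | 100 × 0.030625 × 2 / 0.3 = 20.42 | 0.994 |

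At rho 0.5, an assumed 90 or 80 completers would still give 0.907 or 0.871. The Protocol's own target of 0.80 is met in every case.

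**Step 4. What 100 patients can and cannot detect.** Differences in change, in SD units, with 50 per group:

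| | rho 0.3 | rho 0.5 | rho 0.7 |
|---|---|---|---|
| Detectable with 80% power | 0.670 | 0.566 | 0.438 |
| Power at 0.50 SD | 0.553 | 0.697 | 0.892 |
| Power at 0.35 SD | 0.310 | 0.410 | 0.609 |
| Power at 0.20 SD | 0.133 | 0.168 | 0.248 |

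Sensitivity to differences of about 0.2 to 0.35 SD is therefore low, but neither document claims otherwise in SD units.

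**The case for a change.** The best case for a change is that the label is not merely a tag on f. The authors justify it clinically, by the short intervention and the chronicity of the pain, so it reads as a statement about the treatment effect they hope to see against placebo. On that quantity 0.70 SD sits awkwardly with the words. The Protocol then uses the calculation to declare the sample adequate for the second aim, and gives no SD or point difference that would put a reader right. One sentence would repair this at almost no cost.

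Much of this stands. The translation is absent, the interaction is the natural reading given the comparison with placebo and the mixed ANOVA, and a null result would not exclude 0.2 to 0.35 SD. What does not follow is that the plan is in error. The text ties its label to the f metric, where it is conventional. The mistaken 0.35 SD reading requires someone to ignore the two repeated measures and the correlation given in the same sentence as f. Neither document sets 0.35 SD as a target or plans to treat non-significance as evidence of no effect. To say flatly that the label misdescribes the effect would also go too far, since the interaction is not named and the time effect reproduces 68 as well.

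**Conclusion.** No change is needed. The sample size of 68 is correct for its inputs, and 100 patients deliver more than the stated 80% power at f = 0.175: 93% at the Protocol's rho of 0.5, and 83% to 99% over an assumed 0.3 to 0.7. The regression aim fixed the number recruited, so a different description of f would not alter it, nor the test, nor any figure in the documents.

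What is missing is a conversion that can be derived from the stated inputs. On the interaction reading, f = 0.175 is a 0.70 SD difference in change, and 50 per group can detect about 0.57 SD with 80% power at rho 0.5. An analyst writing up the primary comparison can supply this. At that rho and sample size, the observed difference must reach about 0.40 SD for p < 0.05 (t quantile 1.984 × SD of change 1 × √(4/100) = 0.397), which shows how little a null result would exclude. These figures assume equal groups, a common SD and complete data; losses would raise the detectable difference modestly, to 0.60 or 0.63 SD with an assumed 45 or 40 completers per group.

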## **Dependent variables**

In order to discriminate pain mechanisms between groups of patients, including CS mechanisms, five topics have been identified: clinical examination, questionnaires, quantitative sensory testing, laboratory tests, and imaging tests (Shraim et al., 2021). In the present study, all categories will be taken into account except the last one (only in the case of suspected neuropathic pain)

### *Clinical examination variables*

During the case history taken, data on the characteristics of the patients' CLBP will be collected. Pain intensity will be the main primary outcome. Patients will evaluate the intensity of their CLBP at the current time, as well as the mean, minimum and

maximum pain throughout the preceding seven days or since the time of the previous session, once the study is underway, according to the brief pain inventory (de Andres Ares et al., 2015; Tan et al., 2004). Pain intensity will be collected via an online questionnaire without the presence of any investigator in every visit for descriptive reasons, although only the baseline and the final values will be used for statistical analyses. The other primary outcome will be the degree of disability provoked by CLBP. Upon completing the case history, patients will fill out the Oswestry low back disability index questionnaire (Alcántara-Bumbiedro et al., 2006), which will also be completed at the end of the study.

Additionally, other pain variables will be recorded at baseline for exploratory purposes: CLBP trajectory (duration and frequency) and localization. For the later, patients will draw the area affected by their pain on a tablet, using an application (Symptom Mapper) that will allow the degree of widespreadness of their pain to be calculated (Ellingsen et al., 2021). They may also indicate any pain present of less intensity outside the low back region, as any symptom of higher intensity will necessarily exclude the patient from the study. Additionally, clinicians will determine whether the CLBP is proportionate or disproportionate to the degree or nature of the injury or pathology, with a discrete or rather diffuse distribution, according to criteria that have been defined in the literature (Nijs et al., 2015; Smart, et al., 2012). A diffuse rather than a discrete distribution has been identified as a key criterion suggesting a CS phenotype (Kosek, et al., 2021; Smart, et al., 2012).

Finally, other variables will be reported such as the intake of pain medication compatible with the selection criteria, both at baseline and at the end of treatment. Similarly, whether the patient regularly smokes will be reported at baseline, since smoking has been associated with increased serum levels of pro-inflammatory cytokines.

(Petrescu et al., 2010), and the average number of hours of sleep which may help predict pain patterns and will be used for exploratory purposes (Edwards et al., 2008). Additionally, the presence of any chronic conditions (including pain conditions) that is comorbid with the CLBP will be recorded for exploratory purposes.

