## Project Protocol

### Experimental design

The study consists of a mechanistic randomized placebo-controlled clinical trial with a mixed experimental design, whose objective is to assess which variables that have been linked to central sensitization (CS) in chronic pain patients can predict the response of chronic low back pain (CLBP) patients to spinal manipulative therapy (SMT). In order to do this, clinical, psychophysical and inflammatory variables will be measured in CLBP patients, which will be exposed to either SMT or a placebo SMT for 12 visits over a 4-week period. Another group made up of healthy volunteers will be used to determine the reference values of the same variables in a healthy population and compare them with the clinical population, before and after exposure. The primary outcome measures and main clinical variables are pain intensity and disability. All variables will be measured before the first SMT session, as well as at the end of the twelfth and last session, except for pain intensity, which will be measured at the start of each session for exploratory reasons.

**Figure 1.** Study protocol for the clinical trial

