#### *Adverse events reporting*

At the beginning of any of the follow-up SMT or placebo sessions, each patient will complete an online questionnaire without the presence of the investigator, answering whether they have suffered any adverse effects that they feel could be related to the treatment received. A clinical trial identified the following adverse effects as those most commonly reported after chiropractic treatment based on lumbar SMT: muscle stiffness, increased pain, radiating discomfort, and others (Walker et al., 2013). Following the example of this study, adverse effects will be classified into these categories, in addition to indicating whether they were triggered immediately, up to 24 hours, or more than 24 hours after the previous session, whether their duration was of minutes, hours (< 24 hours), between 24 and 48 hours, or longer than 48 hours (Walker, et al., 2013), and according to their intensity (very mild, mild, moderate, severe, very severe). A 3-point increase in the NRS-11 or the reporting of moderate to severe adverse events in three consecutive visits will raise the alert and the patient will be interviewed to determine whether care should be interrupted.

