## **Procedures**

The study will have a total estimated duration of one year, during which each patient will participate in 12 sessions divided into 3 weekly sessions for 4 weeks (see Figure 1). Once this phase of the study has been completed, patients who had been assigned to the placebo group will be offered the possibility of receiving the equivalent

“real” treatment at the MCC free of charge. Patients who received SMT may continue at their own cost. In addition, 4 weeks after the end of the study, patients will be contacted to request that they provide data on their pain intensity and disability, as described above, as well as responses to the questionnaires proposed as follow-up. Healthy volunteers will participate in two visits, baseline and follow-up after 4 weeks.

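### The two-point primary analysis loses any patient without a session-12 value and shuts out the session scores that could correct for it, and the loss may be related to the outcome

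*Protocol*

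**What the plan says.** Pain intensity and the Oswestry index are the two primary outcomes. Under Clinical examination variables, the protocol collects pain online at each visit, "although only the baseline and the final values will be used for statistical analyses". Its Experimental design section gives the session scores the same exploratory status: "except for pain intensity, which will be measured at the start of each session for exploratory reasons". The Oswestry index is filled in at baseline and again only once, "which will also be completed at the end of the study".

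The SAP states that the two primary outcomes "will be compared between groups (SMT vs. placebo) over time (baseline and session 12) using a mixed analysis of variance". The final value is therefore session 12, not the last value available. The sample size section uses the same two points.

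Under Adverse events reporting, the protocol states: "A 3-point increase in the NRS-11 or the reporting of moderate to severe adverse events in three consecutive visits will raise the alert". What follows is not an automatic stop: "the patient will be interviewed to determine whether care should be interrupted". The Procedures section adds a later contact: "4 weeks after the end of the study, patients will be contacted to request that they provide data on their pain intensity and disability". The SAP gives that contact no place in the primary analysis.

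Neither document defines an analysis population, a missing-data method, a rule for measuring patients whose care stops, or an expected dropout rate.

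**The concern.** In a two-group, two-time mixed ANOVA the group-by-time test is a comparison of change scores. A patient with no session-12 value has no change score and drops out of the comparison. If that value is missing because pain rose and care was interrupted, the patients lost are those with the worst outcomes, and the completers in that arm look better than the arm as randomised.

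At stake is the estimated SMT-versus-placebo difference. If more placebo patients stop for worsening, the difference shrinks. If more SMT patients do, it grows. The scores that would show the worsening are already recorded, but the plan keeps them out of the analysis. Oswestry is more exposed, because it has no intermediate values.

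**Working it through.** **1. The plan's own sample size.** Inputs from the sample size section: f = 0.175, alpha 0.05, power 0.80, 2 groups, m = 2 measures, correlation 0.5. For the interaction, the noncentrality is f² × N × m / (1 − ρ) = 0.030625 × N × 2 / 0.5 = 0.1225 N, with 1 and N − 2 degrees of freedom. N = 66 gives power 0.7997 and N = 68 gives 0.812. The stated 68 is reproduced.

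**2. Power if only completers are analysed.** The plan randomises 100 patients. The documents give no loss rate, so a range is shown.

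| Loss | Completers | Power |
|---|---|---|
| 0% | 100 | 0.934 |
| 10% | 90 | 0.907 |
| 20% | 80 | 0.871 |
| 30% | 70 | 0.823 |
| 35% | 65 | 0.793 |

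Power falls below 0.80 only when about a third are lost. The question is bias.

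**3. Bias by formula.** In one arm, let d be the fraction lost, m the completers' mean change, and g the mean change that lost patients would have shown minus m. The full mean is m + d × g and the completers' mean is m, so the bias is −d × g. Between arms, with a common g, it is −(d_SMT − d_placebo) × g. Negative values favour SMT. All rates and gaps are assumed.

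| SMT lost | Placebo lost | g = 3 points | g = 4.5 points |
|---|---|---|---|
| 5% | 5% | 0 | 0 |
| 10% | 5% | −0.15 | −0.225 |
| 15% | 5% | −0.30 | −0.45 |
| 10% | 20% | +0.30 | +0.45 |

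**4. Main simulation.** Assumptions: 50 per arm, 12 visits, 0–10 scale, SD 2 with half the variance between patients, serial correlation 0.8 in the rest, baseline mean 5.5, placebo change −0.8, 1,500 trials per row. An alert is a rise of at least 3 points from baseline at any of visits 2 to 11. After an alert, care stops with the probability shown, and session 12 is then missing.

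| Stop probability, placebo / SMT | Stopped, placebo / SMT | Full-data difference | Completers' difference |
|---|---|---|---|
| No effect: 1 / 1 | 7.2% / 7.3% | 0.003 | −0.001 |
| No effect: 0 / 1 | 0% / 7.2% | −0.007 | −0.209 |
| No effect: 1 / 0 | 7.4% / 0% | −0.005 | +0.200 |
| Effect: 0.5 / 0.5 | 3.7% / 1.3% | −1.379 | −1.318 |
| Effect: 1 / 1 | 7.3% / 2.5% | −1.356 | −1.222 |
| Effect: 0 / 1 | 0% / 2.6% | −1.352 | −1.430 |

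- With an effect and every alert ending care, attenuation is (1.356 − 1.222) / 1.356 = 9.9%. With half of alerts ending care it is (1.379 − 1.318) / 1.379 = 4.4%.
- The formula agrees. The placebo mean moves from −0.799 to −1.005 (−0.206) and the SMT mean from −2.155 to −2.227 (−0.072). The net shift is −0.072 + 0.206 = +0.134.
- With no effect and only SMT patients stopped, a false benefit of about 0.2 points appears, and the 5% test rejects in 7.3% of trials.
- With no effect and equal stopping, the difference is unbiased, but improvement within each arm is overstated (about −1.00 against −0.79).

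**5. Other assumptions.** A second set used the same baseline and placebo change, visit noise SD 1.0–1.4, patient slope SD 0.10–0.15 per visit, true effects of 0.7 or 1.4, and 400 trials per setting. Attenuation was 2–4% if a quarter of alerted patients stop, 5–8% if half do, and 12–23% if all do. A third set had far heavier loss (8–16% of SMT and 15–23% of placebo patients missing session 12). It gave −0.54 against −0.67, which is 0.13 / 0.67 = 19%, and −1.01 against −1.30, which is 0.29 / 1.30 = 22%.

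**The case against.** The strongest reply is that the documents never say early stoppers go unmeasured. Interrupting care is not withdrawal from measurement. Pain is collected online, Oswestry is due at the end of the study, and patients are contacted again later. If stoppers still give a session-12 value, they stay in the analysis. This stands: the loss is an inference from the stated method together with the absence of any rule for measuring these patients. The later contact does not close the gap, because it lies outside the primary analysis and comes after placebo patients have been offered real treatment.

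A reader might also infer that a 3-point rise ends care. It leads to an interview, and the condition about three consecutive visits can be read as applying to the pain rise as well. Under that reading, the second set of assumptions gave 1–9% attenuation. The wording should be reconciled, but no position is taken on the alert itself.

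Nor do the documents support saying that the planned analysis is biased, or in which direction. Between-arm bias generally needs stopping that differs by arm, and with no effect and equal stopping it was nil.

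Finally, a likelihood model on all visits recovered the full-data effect to within 3% in the third set, but that result is partly built in: simulated stopping depended only on recorded scores. The interview and the adverse-event trigger may bring in information beyond them. This also stands, and is why a sensitivity analysis is needed.

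**Conclusion.** The point holds as a weakness of the stated method, not merely as missing detail. The plan confines the primary analysis to two time points, sets aside session scores that it already collects, and contains a written route by which rising pain may cost a patient the final value. The between-group estimate can then be biased in either direction if stopping differs by arm.

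The size is unknown, because the documents give neither a dropout rate nor a stop rate. Under the assumptions shown, attenuation runs from a few percent to about 20%, with about 10% in the main simulation when every alert ends care. Reaching about 20% took either an interview that always ends care or much heavier loss, and the documents state neither. The stated sample size is correct, and 100 patients leave ample power. The change should be made, but nothing here shows that the trial's result would be wrong.

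**What to change.** 1. Define the primary population as all randomised patients, analysed as assigned.
2. Send the online pain and Oswestry questionnaires at week 4 to every randomised patient, including those whose care stopped, so that both primary outcomes address the same question. State the recall period on the form, because the SAP's pain variable refers back to the previous treatment visit.
3. For pain, replace the two-point ANOVA with a likelihood-based repeated-measures model on all session scores: visit as a factor, group-by-visit, baseline included. Report the session-12 contrast. Name one covariance structure and a fallback in advance; an unstructured matrix over 12 visits has 12 × 13 / 2 = 78 parameters for 100 patients.
4. For Oswestry, use a baseline-adjusted analysis. Where week-4 values are missing, use multiple imputation with the session pain scores as auxiliary variables.
5. Add a sensitivity analysis that treats stopping for worsening as informative, for example by shifting the imputed values of those patients over a pre-stated range. Report stopping by arm and reason.

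The cost is a SAP revision, somewhat more analysis work and one online form for early stoppers. No extra visits or patients are needed, and no change to the clinical alert is proposed.

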## **Healthy population sample**

Additionally, a sample of healthy volunteers will be recruited to be used as a reference for the psychophysical and inflammatory variables collected in the sample of CLBP patients. The reference values obtained from this group will be compared to those of the patient population. To be included in the study, participants must be of legal age (18-70 years old), and present no current or chronic pain condition, as well as not having received any diagnosis of a systemic, inflammatory, neurological or psychiatric condition. They will age/sex matched to the patient group receiving SMT.

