#### *Laboratory tests: inflammatory biomarkers in urine*

Before initiating the first treatment session and on the day of the last one, urine samples will be collected from all patients (first morning micturition), which will be immediately stored at -20°C (see Figure 1–1). Additionally, the first morning micturition will be collected twice from healthy individuals in the same timeframe (two samples with a 4-week delay). Urine concentrations of tumor necrosis factor alpha (TNF- $\alpha$ ) will be measured. For each sample, the urine concentrations of each cytokine (in pg / ml) and creatinine (mg / dl) will be measured. The cytokine to creatinine ratio (in pg / mg) will be calculated to correct for differences in urine volumes (Ortega et al., 2019). TNF- $\alpha$  values will be used for the regression model, since it has been repeatedly found to be elevated in CLBP patients and may respond to a treatment based on SMT (Lim et al., 2020; Morris et al., 2020; Teodorczyk-Injeyan et al., 2006; Teodorczyk-Injeyan et al., 2021).

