In order to interpret the values obtained in patient groups, they will be compared with reference values obtained from the healthy controls to both CLBP groups. This will allow characterizing the patient groups to determine whether they show increased psychological symptoms, increased pain sensitivity and hyperalgesia as well as increased TNF-alpha levels compared with a reference healthy population. In order to do this, a series of mixed analyses of variance will be performed to examine differences in PPTs, urinary TNF- α levels, PCS, CSI, BDI-II and GAD scores before and after treatment between the three groups (control, SMT and placebo). To test a priori hypotheses, significant effects will be decomposed using planned comparisons. For the rest of the effects, Tukey's HSD will be used for testing any pair-wise comparisons between group means.

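### The patient-versus-healthy comparison of TNF-alpha level is not adjusted for smoking, which the protocol records because of its link to cytokines and does not say it will ask of healthy volunteers

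*Protocol*

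**What the plan says.** Under Clinical examination variables, the protocol explains why smoking is collected: "whether the patient regularly smokes will be reported at baseline, since smoking has been associated with increased serum levels of pro-inflammatory cytokines". The sentence refers to patients.

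Under Healthy population sample, the matching is described as "They will age/sex matched to the patient group receiving SMT". Volunteers must "present no current or chronic pain condition, as well as not having received any diagnosis of a systemic, inflammatory, neurological or psychiatric condition", which places no restriction on smoking. Under Sample size calculation, the volunteers' role is to supply "reference values in a healthy population for the predictor variables (questionnaires, PPTs, cytokines only". Neither document says that their smoking status is recorded.

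Under Laboratory tests, the one correction planned for the urinary cytokine is the ratio to creatinine, which "will be calculated to correct for differences in urine volumes".

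The SAP compares the groups by mixed analyses of variance "before and after treatment between the three groups (control, SMT and placebo"), with no covariate named. One purpose is to establish whether patients show "increased TNF-alpha levels compared with a reference healthy population". Smoking appears nowhere in the SAP.

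**The concern.** The protocol names a determinant of the class of biomarker it measures, collects it in patients, and then leaves it out of the analysis where it could do harm. Patients and healthy volunteers are not randomised to be patients or volunteers, so only matching or adjustment can make them comparable on smoking, and the plan provides neither. If smokers are more common among the patients, raised TNF-alpha could be attributed to chronic low back pain when part of it is due to smoking. If smokers are more common among the volunteers, a real elevation could be masked.

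The problem also cannot be mended afterwards if the volunteers are never asked. Recording smoking in patients alone supports description of the two patient arms but not adjustment of the three-group comparison.

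**Working it through.** **The plan's own figures.** The regression rule gives 5 predictors × 10 = 50 per group, as stated. For the mixed analysis of variance with f = 0.175, alpha 0.05, two measures and correlation 0.5, take λ = f²·N·2/(1 − 0.5) with 1 and N − 2 degrees of freedom. Power is 0.7997 at N = 66 and 0.812 at N = 68, so the stated total of 68 is reproduced. This point challenges neither figure.

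**Which TNF-alpha analyses are exposed.** Suppose smoking adds a constant to each smoker's TNF-alpha, on the scale analysed, at both visits.

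- *SMT versus placebo:* smoking is balanced in expectation by randomisation.
- *Group-by-time effect in the three-group analysis:* the constant is present at both visits and drops out of the change.
- *Regression on change in TNF-alpha:* it drops out in the same way.
- *Between-group level, patients versus healthy:* the constant does not cancel. Its contribution is the difference in smoking prevalence times the smoking effect.
- *Regression on baseline TNF-alpha in the SMT arm:* confounding also requires smoking to affect improvement in pain or disability.

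**Inputs for the exposed level comparison.** Group sizes are from the protocol: 100 patients (two arms of 50) and 50 volunteers. The rest is assumed, because the documents give no figure: a smoker shift s of 0.3 to 0.8 SD and a prevalence excess d among patients of 10 to 30 percentage points.

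**Formulas.** Spurious difference b = d × s. For a single visit, SE = √(1/100 + 1/50) = √0.03 = 0.173 SD. The rejection probability at nominal two-sided 5% is P(Z > 1.96 − b/SE) + P(Z < −1.96 − b/SE).

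| Case | d | s (SD) | b (SD) | b/SE | Type I error |
|---|---|---|---|---|---|
| Low | 0.10 | 0.3 | 0.03 | 0.173 | 0.0370 + 0.0165 = 5.3% |
| Middle | 0.20 | 0.5 | 0.10 | 0.577 | 0.0834 + 0.0056 = 8.9% |
| High | 0.30 | 0.8 | 0.24 | 1.386 | 0.2829 + 0.0004 = 28.3% |

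**Sensitivity to the form of the test.** The SAP does not specify the planned contrasts, so other versions were checked for the same three cases.

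| Test | Low | Middle | High |
|---|---|---|---|
| Noncentral t, 100 vs 50, smoking also widening the within-group variance (prevalence 30% vs 20%, 40% vs 20%, 40% vs 10%) | 5.3% | 8.7% | 26.1% |
| Three-group omnibus F, one visit, 50 per group | 5.2% | 7.5% | 21.4% |
| Three-group omnibus F, mean of two visits, correlation 0.5 | 5.3% | 8.4% | 27.4% |
| 100 vs 50, mean of two visits, correlation 0.5: SE = √(0.75 × 0.03) = 0.15 | 5.5% | 10.2% | 36.0% |

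The 0.5 correlation is the protocol's value for the clinical outcomes and is only assumed for TNF-alpha.

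**The baseline predictor in the SMT arm.** The correlation between TNF-alpha and improvement that smoking alone would induce is the product of its correlations with each. For a shift s at prevalence p, each correlation is s√(p(1 − p)) / √(1 + s²p(1 − p)). Assume p of 20% to 40%, a TNF-alpha shift of 0.3 to 0.8 SD and a shift in improvement of 0.3 to 0.5 SD. The lowest case is 0.119 × 0.119 = 0.014 and the highest is 0.365 × 0.238 = 0.087.

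**The case against.** The strongest reply is that this is a supportive comparison with an unquantified confounder. The SAP introduces the healthy group to help interpret the patients' values, and pain, disability and both sample-size calculations are untouched. Every figure for the bias rests on assumption, including its direction. The protocol's rationale concerns serum, whereas the trial measures a urinary ratio to creatinine, and whether the effect carries over is unknown. At the low end there is practically no inflation, and the high end needs the largest effect and the largest gap together. All of this stands. It limits the weight of the point but does not remove it, since the protocol considered the link strong enough to collect the variable.

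A reader might go further and infer that TNF-alpha as a predictor of response is merely standing in for smoking. The documents do not support that. They link smoking to cytokines, not to improvement in pain or disability, and confounding of the regression needs both links. Even granting the second, the induced correlation is about 0.01 to 0.09. For prediction alone, a marker that varies partly with smoking is still a legitimate predictor; only a causal reading would be affected.

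A reader might also infer that volunteers will certainly not be asked about smoking. The restriction to questionnaires, PPTs and cytokines describes which predictor variables receive reference values and need not be a complete data-collection list. What can be said is that the documents do not state that volunteers' smoking is collected.

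**Conclusion.** The point holds for one analysis: the between-group level of TNF-alpha, patients against healthy volunteers. That contrast is open to a confounder the protocol itself names, with no matching, adjustment or stated collection in the volunteers. Under the assumed ranges the spurious difference is 0.03 to 0.24 SD, and the type I error of a single-visit 100-versus-50 contrast is about 5% to 28%, with about 9% in the middle case. Other reasonable forms of the test give the same order of magnitude. The true size cannot be derived from the documents.

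The finding does not extend to the randomised comparison. Nor does it extend to the group-by-time and change analyses, provided the smoking effect is additive and stable over the 4 weeks. For the baseline predictor the expected confounding is small. This is an inexpensive improvement to a secondary comparison and does not threaten the primary results.

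**What to change.** Ask healthy volunteers at baseline the same yes/no question on regular smoking that patients are asked, and say so in the protocol. This step is time-critical, because adjustment is impossible without it. In the SAP, add smoking (yes/no) as a covariate in the three-group TNF-alpha analysis, and report the proportion of smokers in each of the three groups. The cost is one question, one degree of freedom and a line of SAP wording.

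Optionally, repeat the SMT-arm regressions containing baseline TNF-alpha with smoking added, labelled as a sensitivity analysis only. A sixth predictor would need 6 × 10 = 60 patients under the protocol's own rule, against 50 planned (50/6 = 8.3 per predictor), so the main models should keep their five.
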